6.3.2 Security Measures

Data will be securely stored on two secure electronic systems that use encryption: Research Electronic Data Capture (REDCap) and University of Arizona Box Health (UA Box Health). REDCap will be primarily used to store informed consent and parental permission PDFs, demographics, health data extracted from medical records, and completed questionnaires. Within REDCap we use Twilio for daily text messaging with participants. UA Box Health will be used to store video-recordings, behavioral coding of the content within video recordings, and results of laboratory analyses. All electronic data outside of these systems will have unique anonymous codes.

All study laptops and tablets will use password encryption. A second password will be required to open study databases. The College of Nursing (CON) network is located behind a campus administered firewall. The CON systems are on a "private IP" net and access from outside is tightly controlled at the Firewall. Traffic from Outside to Inside network is blocked and only ports required for normal operations and special purpose ports for applications/services are allowed for outside access. There is also an Intrusion Detection System, and it is regularly monitored for security breaches. Wireless network traffic is isolated from Wired network traffic.

In addition to electronic data, hard copy data, such as informed consents and parental permissions, will be locked in a cabinet within the PI's locked office within the CON. Separate from identifiable data, is another locked cabinet within a locked CON office for data with unique anonymous codes. Only the PI and program coordinator will have access to these locked file systems. Laboratory specimens (labeled with unique anonymous codes) will be processed and stored in freezer systems within locked keycard access rooms at the UA College of Nursing, Biological Core Laboratory. Freezers are continuously monitored with a malfunction alarm system. The Biological Core Laboratory will also conduct the analyses of oxytocin receptor gene expression and oxytocin receptor protein. Samples will be transported on dry ice to the UA Genetic Core for analysis of oxytocin receptor gene methylation. Samples will be transported on dry ice to the UA Laboratory for the Evolutionary Endocrinology of Primates (LEEP) for analysis of oxytocin peptide.

6.3.3 Data Handling Practices

Medical record data from recruitment sites (Banner University Medical Center and Tucson Medical Center) will be viewed in the electronic systems and entered directly into REDCap/Box-Health using password encrypted laptops or tablets. Pre-screening procedures (as described in the section below on data confidentiality) will not use paper but will be entered in a password protected EXCEL file stored on the encrypted UA Box Health. PHI collected on paper (e.g., informed consents and parental permissions) will be kept in a locked cabinet in a locked office at the College of Nursing; PDFs are created and uploaded into REDCap. The scanner in the College of Nursing suite is encrypted. Data from questionnaires and information from mothers collected at study sessions will also be entered directly into REDCap. Blood and saliva specimens are labeled with unique codes without identifiable information and hand delivered on ice by a research team member from the data collection room (2nd floor of the College of Nursing) to the Biological Core Laboratory (4th floor of the College of Nursing) for processing and secure storage. Electronic video recordings of mother-infant interaction at the final data collection session will be labeled with unique codes without identifiable information and stored on the encrypted UA Box Health for coding of data. Complying with federal guidelines, raw data (including video recordings and biological specimens) will be destroyed three years after submission of our final NIH report.

6.3.4 Quality Assurance Measures

To ensure quality of data and compliance with IRB requirements, the following procurees will be followed:

- The PI will audit the informed consents/parental permissions in each of the first 20 enrolled participants and then 20% of enrolled participants throughout the study period.

- The PI and [REDACTED] will train to criterion the ATVV to research personnel ([REDACTED] and [REDACTED]) and check inter-rater reliability in the first 10 enrolled participants and 20% of all sessions throughout the study period.
- The PI will audit the first 10 sequential data collection visits and then 20% of all sessions throughout the study period.
- The PI will train (blinded to group assignment) research personnel coding video-recordings for mother-infant synchrony to > 90% inter-rater reliability by the end of their training period. [REDACTED] will audit 20% of all video-recordings and recode them to maintain reliability.

6.3.5 Data Confidentiality

To minimize risk related to loss of confidentiality, the PIs and other authorized study personnel will have IRB required training in recruitment, informed consent procedures, human subjects Research, HIPAA, and data management using the institution's training modules and certifications. No information about participants during the research will be disclosed to others without a participant's written permission, except if necessary to protect their rights or welfare or if required by law. Only aggregate data will be published or discussed in conferences, and no individual information will be included that would reveal a participant's identity. Secure electronic systems (REDCap and UA Box Health) are described above in the section on data security.

6.4 Identifying, Reviewing, and Reporting Adverse Events and Unanticipated Problems

6.4.1 Definitions

6.4.1.1 Adverse Events

Adverse event means any untoward medical occurrence associated with the use of an intervention in humans, whether considered intervention related or not. According to the UA IRB, an **adverse event (AE)** is further explained as an untoward physical or psychological occurrence in a human subject participating in research which occurs during the study having been absent at baseline or, if present at baseline, appears to worsen. The event may be any unfavorable outcome, including abnormal laboratory result, symptom, disease, or injury.

6.4.1.2 Serious Adverse Events

Adverse events classified as serious include those resulting in death, life-threatening injury, hospitalization, or prolongation of hospitalization, persistent or significant disability, or a congenital anomaly or birth defect. Events not meeting the above criteria but requiring intervention to prevent one of these outcomes are also considered serious adverse events.

6.4.1.3 Unanticipated Problems

According to the UA IRB, **unanticipated problems** involving risks to subjects or others refers to a problem, event or information item that is unexpected, given the nature of the research procedures and the subject population being studied. Potential risks associated with participating in this study have been delineated in section 2.2.

6.4.2 Procedure to Classify an Adverse Event

AEs are classified into the following three categories-

- **Mild** – Events require minimal or no treatment and do not interfere with the participant's daily activities. Because this study has been classified by the IRB as research involving no more than minimal risk (Appendix A – Approval Documents), we will not document mild adverse events.

- **Moderate** – Events result in a low level of inconvenience or concern with the intervention. Moderate events may cause some interference with functioning.
- **Severe** – Events interrupt a participant's usual daily activity and may require systemic drug therapy or other treatment. Severe events are usually potentially life-threatening or incapacitating. Of note, the term "severe" does not necessarily equate to "serious".

In the past 35 years of NIH-funded research with the ATVV, there has not been an adverse event directly related to the ATVV intervention, even when infants with brain injury were enrolled. This study will enroll low risk healthy mothers and infants. Infants are excluded from the study if born with a significant congenital anomaly or birth defect. If a specific safety concern is identified by research team members during enrollment, the weekly phone calls, or monthly study visits, (either for the infant and/or the mother) team members will

- document the event or problem using the [Adverse Event Report](#) form,
- follow the protocol as outlined in section 6.2 on minimizing risk which indicates to meet and discuss any AE as a team, and
- report severe events to the PI per instructions at the top of the AE Report.

If there is an immediate safety concern for the mother and/or the infant, the team member consult with the PI. The PI will convene a meeting with the SMC for any moderate or serious adverse events or unanticipated problems. The NIH Guidance on Reporting Adverse Events to IRBs for NIH Supported Multicenter Clinical Trials will be followed. The UA IRB has established policies for 1) reporting unanticipated problems and 2) handling complaints and non-compliance with human subject protection regulations. We will adhere to UA IRB instructions on how to report problems and adverse events, found at <https://rgw.arizona.edu/compliance/human-subjects-protection-program/guidance-researchers>. The IRB lists events that require reporting within 5 business days of the PI becoming aware (e.g. serious adverse events or serious unanticipated problems), events that require reporting within 15 business days of the PI becoming aware (e.g. adverse events or problems that indicate a greater risk of harm than previously known), and events that do not require reporting (e.g. adverse events or problems not associated with greater harm than previously known).

In summary, this is a minimal risk protocol for injury or adverse events. We have never had an adverse event with the premature infants in our research. For full term infants, there is no anticipated physical risk. Safety assessments and monitoring are incorporated into the project. If a physical risk occurs, the case will be reviewed by the SMC and guidelines established for future review.

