4.4 Attention-Control Comparison

4.4.1 Description of Attention-Control Group.

The Attention Control group is designed to provide a similar amount of research staff attention while in the hospital after birth, during weekly phone calls, and at 3 postnatal study visits but with the focus on didactic education (content distinctly different from the intervention). The Attention Control education protocol has been used for over 15 years in three of our previous RCTs, demonstrating acceptability to mothers, easy implementation, and rigor in isolating the impact of ATVV.^(28-30, 78) In our Attention Control, mothers will receive education on safe infant care including content on diapers, infant clothing, blankets, bathing, sleep positions, sleep habits, holding the baby, safety of infant equipment, breastfeeding, formula, and age-appropriate toys. The research member will use a prepared script and record in the Attention Control Record the information discussed. Since the ATVV intervention mothers will be contacted by a weekly phone call, the research member will also contact the Attention Control mothers by weekly calls to reinforce education. For both groups, weekly calls will include standard milestones in infant development.

4.4.2 Administration of Attention-Control Group.

The Attention-Control group is administered by the Research Assistant. An Attention-Control manual similar in appearance to the ATVV manual but differing in content is provided to mothers while they are in the hospital prior to discharge. Review of the infant care material while in the hospital is of equivalent time as required to instruct the ATVV Intervention group. The Attention-Control group also receives weekly phone calls to discuss topics of their request regarding infant care and development. We maintain focus on care and away from the mother-infant relationship. Questions regarding breastfeeding are referred to their primary care physician or other resources.

At the monthly visits and weekly phone calls with mothers in the attention control group, we will reinforce education on safe infant care (including content on diapers, infant clothing, blankets, infant care including bathing, sleep positions, sleep habits, holding the baby, safety of infant equipment, breastfeeding, formula, and age-appropriate toys). We will also include standard milestones in infant development for both groups.

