4.6.2 Division of Responsibilities

The Attention Control Educator (██████████) teaches infant care to the Attention Control women before hospital discharge. Similarly, the ATVV Intervention Educator (██████████) teaches ATVV to the ATTV women before hospital discharge. Instruction for both group conditions take approximately 30 minutes. To prevent bias, only Attention Control Educators will work with the Attention Control group, and only ██████████ will work with the ATVV group. The Program Coordinator assists with baseline data collections as needed to maintain this division of responsibility. However, personnel management and participant-language needs necessitate some flexibility.

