6.5 Procedures for multi-site studies to ensure compliance with the DSM plan

This is not a multi-site research project. [REDACTED]

[REDACTED] Collaborators will follow the UA IRB approved protocol for safe and secure handling of specimens and video recordings labeled with unique anonymous codes. Collaborators will not have access to participant identifiers. Data will be shared using the UA Box Health cloud-based secure system. Collaborators must complete comprehensive training and be invited to collaborate on UA Box Health.

6.6 Assessment of external factors that may impact safety or ethics of the study

We have not identified any external factors, such as developments in the literature, that may impact the safety of participants or ethics of the study. Infant massage is a common practice worldwide, and our expanded infant massage version (which includes attention to infant cues, eye contact, talking and rocking) is typically enjoyable for mothers and infants. We check intervention fidelity at each monthly study visit, as well as ask mothers how the intervention is going at each weekly phone call. If external factors are identified, the PI and SMC will discuss with NINR appropriate changes to protocol.

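### Adverse events are recorded only when staff spot a concern, mainly arm-specific staff in contacts whose content differs by arm, so counts are open to under-ascertainment and to differential ascertainment of unknown size and direction

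*Combined protocol and SAP*

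**What the plan says.** Section 6.4.1.1 defines an adverse event broadly, covering any untoward occurrence whether or not it is linked to the intervention. The operational rule in Section 6.4.2 is narrower. Team members complete an Adverse Event Report "If a specific safety concern is identified by research team members during enrollment, the weekly phone calls, or monthly study visits". The same section says of mild events that "we will not document mild adverse events", and opens its definition of moderate with "Events result in a low level of inconvenience or concern with the intervention". It later states that "Safety assessments and monitoring are incorporated into the project", but the Schedule of Events (Section 1.4) shows no adverse-event assessment at any time point.

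On who makes the contacts, Section 4.6.2 says "To prevent bias, only Attention Control Educators will work with the Attention Control group", with a parallel restriction for the ATVV arm and an allowance for exceptions on staffing and language grounds.

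On what the contacts contain, Section 4.3 has staff review use of the massage and barriers to it at weekly calls and monthly visits, and Section 5.3 retests the mother's technique at months 1, 2 and 3. Section 6.6 says that staff "ask mothers how the intervention is going at each weekly phone call". For controls, Section 4.4.2 says "The Attention-Control group also receives weekly phone calls to discuss topics of their request regarding infant care and development", and staff are to steer clear of how mother and infant relate. Section 4.4.1 matches the amount of attention in hospital, by telephone and at the three postnatal visits.

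On use, the Safety Monitoring Committee audits adverse events (Section 6.2), is convened for moderate or serious ones (Section 6.4.2), and monitors them for a futility assessment together with recruitment and retention (Section 6.7). Section 4.8 plans no between-arm analysis of adverse events.

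**The concern.** A process triggered by a staff member's concern does not reliably deliver the broad definition in Section 6.4.1.1. Events that nobody asks about, and that the mother does not volunteer, are lost in both arms. That alone weakens a statement that no events occurred.

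The second problem is between arms. The people who decide whether something is a concern mostly work in one arm and know which. They hear different conversations and, in the ATVV arm, also watch the mother's technique each month; no matching observation of controls is described. They then apply a recording threshold whose moderate category is framed around the intervention. The line between mild and moderate decides whether an event is documented at all, and that framing has no clear meaning for a control mother. The same event could therefore have a different chance of being recorded in each arm.

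**Working it through.** The plan states no adverse-event rate, detection probability or safety sample size, so there is no figure to reproduce. The check has two parts.

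**Part 1: the elements of ascertainment, side by side**

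| Element | ATVV arm | Control arm | Source |
|---|---|---|---|
| Occasions and amount of contact | Hospital, weekly calls, 3 visits | The same, by design | 4.4.1 |
| Staff | Own educators, exceptions allowed | Own educators, exceptions allowed | 4.6.2 |
| Content of contacts | Use, barriers including infant state, technique | Infant-care and development topics the mother requests | 4.3, 5.3, 4.4.2 |
| Scripted adverse-event question | None described | None described | 1.4, 6.4.2 |
| Recording threshold | Mild not documented; moderate refers to the intervention | Same words, unclear application | 6.4.2 |

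Occasions match. Staff and content do not, and the threshold is worded asymmetrically. Differential detection is therefore plausible, but nothing in the table shows which arm would be favoured.

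**Part 2: what unequal detection would do**

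Let the true risk be *r* in both arms and the detection probabilities *d*A (ATVV) and *d*C (control). Then

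- observed risk = *r* × *d*
- observed risk ratio = (*r* × *d*A) / (*r* × *d*C) = *d*A / *d*C
- expected recorded events = 125 × *r* × *d*, using the 125 randomised per arm (Section 4.6.1) before attrition.

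Assume *r* = 10%, so 125 × 0.10 = 12.5 true events per arm. All values of *r* and *d* are assumptions.

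| *d*A / *d*C | Recorded, ATVV vs control | Observed risk ratio | Risk difference (points) |
|---|---|---|---|
| 90% / 90% | 11.25 vs 11.25 | 1.00 | 0 |
| 50% / 50% | 6.25 vs 6.25 | 1.00 | 0 |
| 90% / 70% | 11.25 vs 8.75 | 1.29 | +2 |
| 70% / 90% | 8.75 vs 11.25 | 0.78 | −2 |
| 90% / 50% | 11.25 vs 6.25 | 1.80 | +4 |
| 50% / 90% | 6.25 vs 11.25 | 0.56 | −4 |

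If someone tested such counts at two-sided 5%, the chance of a false difference would be about 8% for the 90/70 pair and 24% for the 90/50 pair at *r* = 10%. It would be about 6% and 14% at *r* = 5%, and 14% and 45% at *r* = 20%.

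The 50/50 row separates the two problems. Unsolicited collection halves the count with no distortion of the ratio; distortion needs detection that differs by arm.

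**The case against.** The case for leaving the plan alone has several parts.

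- **Contact is matched, and the trigger is not restricted by arm.** This is correct. Section 4.4.1 equalises the occasions, Section 6.4.2 applies to mother and infant in both arms, and staff separation is not absolute. But matching covers the amount of attention, not what is asked or observed.
- **Structured data are collected without restriction by arm.** The mood, stress and parenting-stress questionnaires and the follow-up questionnaires (Section 1.4), health status (Section 4.5) and an identical daily text with a stress item (Section 4.3) all exist. No section says that they feed adverse-event reporting.
- **The direction is open.** This stands. Questions about barriers to massage are not health questions, and a merely unsettled infant would probably count as mild. Control calls on sleep, feeding and equipment safety could bring out illness or injury as readily.
- **The moderate definition has a second sentence, on interference with functioning, that fits either arm.** This softens the wording problem but does not remove it.
- **An unseen procedure may contain a script.** Section 2.2.2.3 cites an Adverse Events procedure, there for emotional distress, and Section 6.4.2 links a report form. If either holds a common question, the sponsor need only cite it.
- **The trial is minimal risk.** This argues for modest priority, not for unequal ascertainment.

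A reader might infer from Section 6.6 that only ATVV mothers are asked each week how things are going, so that one arm is prompted and the other never is. The paragraph concerns the massage, which makes this a fair guess, but the text says mothers without naming an arm. Section 4.1.6.4 also has both groups receive feedback on their experience at monthly visits.

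**Conclusion.** The point holds as a cheap improvement. As described, adverse-event capture is unsolicited, runs mainly through staff who know the arm, and rests on contacts with different content and a threshold worded around the intervention. The counts that reach the committee and the futility assessment, and any by-arm report, are open to under-ascertainment and to differential ascertainment.

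The size and direction are unknown. The table of risk ratios illustrates a mechanism and does not estimate this trial's bias. It assumes equal true risk and chosen detection probabilities, none of which the documents supply.

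A reader might go further and conclude that event rates cannot be compared between arms, or that an excess in the ATVV arm should be expected. The documents support neither. A comparison would be possible but open to bias, Section 4.8 plans none, and the committee and futility uses are not described as comparing arms. The verdict also assumes that no unseen procedure already provides a common question.

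**What to change.** 1. Add one identically worded question to the weekly-call and T1 to T3 visit scripts of both arms, for example: *Since we last spoke, have you or your baby had any illness, injury, hospital visit or other health problem?* Enter the answer in a REDCap field and add a row to the Schedule of Events. If an existing procedure already contains such a question, cite it instead.
2. Word the severity categories without reference to the intervention, so that they read the same way for both arms.
3. Tabulate events by arm from the scripted contacts, and list events found in other ways separately.
4. For participants followed before the change, state the unsolicited collection method and its limits wherever adverse events are reported by arm.

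The cost is a script change and one data field, within contacts that are already scheduled. Calls become slightly longer. More events will be recorded and reviewed, including by the committee, which Section 6.4.2 convenes for any moderate or serious event.

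Timing limits the benefit. The document is version 1.6, dated 31 January 2024; Section 1.2 projects the end of data collection for 31 March 2024, and Table 5 shows births ending in November to December 2023. A new question would reach only the last contacts and would mix two collection methods, so results should be shown separately for the periods before and after the change. For most participants, item 4 is the part that can still be carried out.
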